13.1 Overview

The primary objective of this pilot study is to establish a range of German cockroach doses that, when delivered intranasally, can induce a positive response to NAC in adults (TNSS ≥ 8 out of 12 or a sneezing score of 3) and children (TNSS ≥ 6 out of 12 or a sneezing score of 3). Other secondary objectives are to determine whether these doses are safe, to test the validity of objective outcomes of nasal challenge, and to assess the reproducibility of the nasal challenge.

13.2 Outcomes

13.2.1 Primary Outcomes

The primary outcomes are:

1. The prevalence of positive NAC, defined as a sneezing score of 3 or a TNSS ≥ 8 out of 12 in Phase 1 or a TNSS ≥ 6 out of 12 in Phase 2.
2. The number of reported adverse events and serious adverse events, including their severity, seriousness, and treatment relatedness.

13.2.2 Secondary Outcomes

1. Number of sneezes.
2. Maximum TNSS recoded out of all doses received.
3. Change in TNSS.
4. Change in PNIF.
5. Change in PEF.
6. Visual Analog Scale (VAS).
7. Change in tryptase in nasal secretions
8. Change in albumin in nasal secretions

13.2.3 Exploratory Outcomes

1. Change in chemokines in nasal secretions
2. Change in cockroach-specific T-cell epitopes in peripheral blood

13.3 Measures to Minimize Bias

This is a one arm open label study without randomization. All laboratory assays for tryptase and albumin will be performed in a central laboratory.

13.4 Analysis Plan

13.4.1 Analysis Populations

The study population consists of adults aged 18 through 55 years (phase 1) and children ages 8 through 14 years (phase 2) who have a history of asthma and are German cockroach sensitive. The study will examine the safety of the administration of non-standardized German cockroach extract delivered intranasally. This is a phase I safety pilot study with no efficacy measures; thus, only one analysis population, the safety population, will be defined for this study. The safety population will include all study participants who receive the initial dose during the Challenge Visit. All statistical analyses will be performed on the Safety Population.

13.4.2 Primary Analysis of Primary Outcomes

The first primary objective of this analysis is to estimate a probability of positive response at each dose, defined as reaching a sneezing score of 3 or a TNSS of ≥ 8 in Phase 1 or a TNSS of ≥ 6 in Phase 2. The probability of reaching a positive response will be estimated using the percentage of responses in subjects at each of the 9 doses. Although a participant will stop receiving doses once they have reached a sneezing score of 3 or a TNSS of ≥ 8 in Phase 1 or a TNSS of ≥ 6 in Phase 2, it is assumed that they would continue to respond for the remaining doses. Therefore, if 7 people respond prior to Dose 5, 3 will be tested at Dose 5, and the proportion presented for Dose 5 would be $(7 + \# \text{ responders at Dose 5})/10$. Associated exact 95% confidence intervals will be estimated using the Clopper-Pearson method.

The second primary objective of this analysis is to assess if intranasal delivery of cockroach allergen via a nasal allergen challenge is safe. This will be done by determining the rate of related adverse events and serious adverse events in the course of treatment. Frequency of AEs and SAEs will be tabulated by event, organ, seriousness, severity, and treatment relatedness.

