	asthma ages 8-14 years who will undergo a nasal allergen challenge using the dose range identified in Phase 1a. The threshold for a positive response to the NAC in Phase 2 will be lowered to a TNSS ≥ 6 ; the sneezing score of 3 will remain the same.
Primary Outcomes	
 1. Prevalence of a positive response to NAC, defined at each dose as any sneezing score of 3 or a Total Nasal Symptom Score (TNSS) ≥ 8 out of 12 in Phase 1 or a TNSS ≥ 6 out of 12 in Phase 2. 2. The number of reported adverse events and serious adverse events, including their severity, seriousness, and relatedness
Secondary Outcomes	
 1. Number of Sneezes 2. TNSS – highest score out of all doses received 3. TNSS – change from baseline 4. Change in PNIF from baseline 5. Change in PEF from baseline 6. Visual Analog Scale (VAS) - change from baseline 7. Change in tryptase in nasal secretions 8. Change in albumin in nasal secretions
Exploratory Outcomes	
 1. Change in chemokines and other biomarkers in nasal secretions 2. Change in cockroach-specific T-cell epitopes in peripheral blood
Accrual Objective	35 (Phase 1 - 10 adults, Phase 2 - 25 children)
Study Duration	1 year
Treatment Description	Participants will receive escalating doses of glycerinated German cockroach allergenic extract administered via the intranasal route.
Inclusion Criteria	
Individuals who meet all of the following criteria are eligible for enrollment as study participants for Phase 1a and Phase 2:
 
 1. Subject and/or parent guardian must be able to understand and provide informed consent 2. Male or female adults, 18 through 55 years of age at recruitment (Phase 1) or male or female children, 8-14 years of age at recruitment (Phase 2). 3. Have a history of asthma for a minimum of 1 year before study entry. 
 a. A diagnosis of asthma will be defined as a report by the participant that they have had a clinical diagnosis of asthma made by a physician over a year ago. b. The participant must have persistent asthma

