1.4. Clinical Studies

There have been three reports of nasal allergen challenge with cockroach extract in the literature.⁵⁻⁷

In the Hosen study, 174 patients of unreported ages underwent nasal provocation testing to insects common to Texas. An unclear number of these patients underwent nasal provocation testing specifically to cockroach. The extract used as the diagnostic agent was a powdered concentration of cockroach, which was directly inhaled by the patients in the setting of nasal allergen challenge with multiple allergen extracts in powdered form. Participants would be treated with phenylephrine hydrochloride and, if needed, a bronchodilator in between allergen challenges. Sixty nine patients were reported to have had a systemic reaction to 1 of the allergen extracts. For cockroach in particular, 16 total reactions were reported, of which 11 were nasal, 2 were listed as bronchial asthma, and 3 were listed as post-nasal and upper bronchial.⁷

In the Okuda study, 560 patients from the ages of 4 to 80 years old (mean 31.3 years; 112 participants were 19 years old or younger) with allergic rhinitis were recruited to undergo an evaluation for insect allergy. Sixty-five participants of unknown ages were selected by unspecified means from the pool of 560 patients to undergo nasal allergen challenge with a mixture of German cockroach, *Chironomus yoshimatsui*, and silkworm moth. The publication did not mention whether there were any adverse reactions from the nasal allergen challenge.⁵

The most recent and informative study evaluated the concept of localized allergy in patients with nonallergic rhinitis. In that study, 16 adult volunteers underwent sequential nasal allergen testing with a variety of aeroallergens, including a cockroach extract mix. The cockroach mix nasal allergen testing was done with an arbitrarily chosen single dose of 100 μ L of 1:5000 (w/v), and no testing was conducted prior to the challenge to establish a dose. No adverse events were reported in this published report.⁶

For further details, please refer to the Investigator Brochure for German Cockroach Allergenic Extract for Nasal Allergen Challenge.

2. Study Hypotheses/Objectives**2.1. Hypotheses**

The two hypotheses tested by this study are: intranasal delivery of cockroach allergen via a nasal allergen challenge 1) can induce significant changes in nasal symptoms and 2) can be safely administered in adults and children with asthma.

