3.2. Primary Outcomes

- 1) Prevalence of a positive response to NAC, defined at each dose as any sneezing score of 3 or a TNSS ≥ 8 out of 12 in Phase 1 or a TNSS ≥ 6 out of 12 in Phase 2.
- 2) Safety - number of reported adverse events and serious adverse events, including their severity, seriousness, and relatedness to study procedures.

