8.2 Primary Adverse Events Endpoints

All AEs will be classified by system organ class (SOC) and preferred term, according to a standardized thesaurus (Medical Dictionary for Regulatory Activities [MedDRA] version 18.1). The severity of AEs will be classified, as applicable, using the following grading scales:

- The National Cancer Institute's Common Toxicity Criteria for Adverse Events version 4.03.
- Grading scale of local reactions related to the Nasal Allergen Challenge or skin testing.
- Declines in PEF during the Nasal Allergen Challenge visit
- Grading system of severity of anaphylaxis

Each AE is entered on the electronic case report form (eCRF) once at the highest severity.

An overall summary table will be developed to report the number of events and the number and percentage of subjects having at least one event in the following categories:

- AEs
- AEs indicated as serious
- AEs that lead to study drug discontinuation
- AEs with an outcome of death
- AEs that were reported as being related to a study drug, including instances where PEF declined by more than 20% from baseline
- AEs reported by maximum severity on each applicable grading scale.

Summary tables will present the total number of events as well as the number and percentage of subjects experiencing the events. If a subject experiences the same AE on multiple occasions, the event will be counted once for each occurrence when reporting the number of AEs. When reporting the number of subjects experiencing the events, a subject will only be counted once if they experience an event within the particular SOC or preferred term. Percentages will be based on the number of subjects in the safety population.

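### The co-primary safety outcome is to be reported without any measure of uncertainty, although exact intervals are planned for the response co-primary in the same 10 adults and 25 children

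*Protocol*

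**What the plan says.** Safety is one of two primary outcomes. Protocol 3.2 lists it as "Safety - number of reported adverse events and serious adverse events", with severity, seriousness and relatedness. It is also one of the two hypotheses in Protocol 2.1, namely that the challenge "can be safely administered in adults and children with asthma".

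Protocol 13.4.2 puts this as a question to be answered: "The second primary objective of this analysis is to assess if intranasal delivery of cockroach allergen via a nasal allergen challenge is safe". The method follows: "This will be done by determining the rate of related adverse events and serious adverse events", and then "Frequency of AEs and SAEs will be tabulated by event, organ, seriousness, severity, and treatment relatedness".

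SAP 8.1 analyses safety separately in Phase 1a, Phase 1b and Phase 2 and adds listings. SAP 8.2 adds an overall summary (serious events, deaths, discontinuations, related events including PEF falls of more than 20%, maximum severity) and states: "Summary tables will present the total number of events as well as the number and percentage of subjects experiencing the events". On the denominator it says: "Percentages will be based on the number of subjects in the safety population". SAP 8.3 treats SAEs in the same way.

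Neither document plans a confidence interval or upper bound for any AE or SAE proportion, and neither sets a rate below which the challenge would count as safe.

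**The concern.** The two primary outcomes are handled differently in adjoining paragraphs of Protocol 13.4.2. Positive response gets exact 95% Clopper-Pearson intervals, repeated for both cohorts in SAP 7.1.5. Safety, in the same participants, gets none. The SAP plans 95% intervals even for secondary outcomes: maximum TNSS (7.2.2), change from baseline in six variables (7.2.3), and the Phase 1a versus 1b difference (7.2.4).

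The sample size does not fill the gap. Protocol 13.6 rests it on the response outcome and justifies the 25 children by the need for more dosing information.

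At stake is how the pilot is used. Protocol 1.1 says it will inform whether and how the procedure enters a later large immunotherapy trial, and Protocol 4.1 places that trial in inner-city children with asthma. A cell showing no events in 25 children, with nothing beside it to say what that rules out, is weak support for such a decision and is easily over-read.

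**Working it through.** **Inputs from the documents**
- Group sizes: 10 adults and 25 children (Protocol synopsis, accrual objective; Protocol 13.6).
- Interval method: exact two-sided 95% Clopper-Pearson (Protocol 13.4.2; SAP 7.1.5).
- Strata: Phases 1a, 1b and 2 analysed separately, not pooled (SAP 8.1).

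**Input that is assumed**
- True per-participant event rate: the documents give none, so 5%, 10% and 20% are shown as a range.

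**Step 1: reproduce the plan's own figures.** For x events in n participants, the lower limit is the 0.025 quantile of Beta(x, n − x + 1) and the upper limit is the 0.975 quantile of Beta(x + 1, n − x). All 11 rows of the table in Protocol 13.6 reproduce to the stated rounding. For example:
- 0/10: upper limit 0.3085 (stated 0.31)
- 1/10: 0.0025 to 0.4450 (stated 0.003 to 0.45)
- 10/10: lower limit 0.6915 (stated 0.69)

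That table is for positive response, but the arithmetic is the same for any yes/no outcome per participant.

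**Step 2: apply the same method to adverse events.** With x = 0 the upper limit reduces to 1 − 0.025^(1/n).
- n = 10: 1 − 0.025^(1/10) = 1 − 0.6915 = 30.8%
- n = 25: 1 − 0.025^(1/25) = 1 − 0.8628 = 13.7%

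One event gives:
- 1/10 = 10% (0.25% to 44.5%)
- 1/25 = 4% (0.1% to 20.4%)

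Pooling all 35, which the SAP does not plan, would still leave an upper limit of 10.0% for 0/35.

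**Step 3: chance of seeing no event.** P(0) = (1 − p)^n.

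| Assumed true rate p | n = 10 | n = 25 |
|---|---|---|
| 5% | 0.95^10 = 59.9% | 0.95^25 = 27.7% |
| 10% | 0.90^10 = 34.9% | 0.90^25 = 7.2% |
| 20% | 0.80^10 = 10.7% | 0.80^25 = 0.4% |

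**Step 4: where the zero-event case is realistic.** Under Protocol Table 12.3.1a a grade 1 local reaction to the challenge needs only rescue antihistamines, decongestants or nasal steroids, and Protocol 7.4 allows antihistamines or a nasal steroid afterwards. Zero participants with any related AE is therefore not the natural expectation. Zero is plausible mainly for SAEs and systemic reactions. For related AEs the interval is still needed, but to show the precision of a non-zero proportion.

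**The case against.** The strongest reply is that this is a descriptive pilot with adequate descriptive tables. Protocol 2.2 asks only that the safety profile be documented. The tables cover counts, participants affected, severity, seriousness and relatedness, so it would be wrong to infer that the plan offers nothing but bare percentages. A reader given the count and denominator can work out an exact interval. Participants are protected by the stopping rules in Protocol 11.5, where a single possibly related non-fatal SAE suspends enrolment and treatment, and by DSMB review (Protocol 12.8.2).

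Much of this stands. No procedure is unsafe because an interval is missing, and no data are lost. But stopping rules and DSMB review decide whether the study pauses; they do not say how the final safety result is estimated or worded. The descriptive objective in 2.2 also sits beside 2.1 and 13.4.2, which ask whether the challenge is safe. Protocol 13.1 muddies this further by listing safety among the secondary objectives, against 2.2, 3.2, 13.2.1 and 13.4.2.

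Three stronger readings are tempting, and the documents do not support them.
- *The plan will declare the challenge safe if no events occur.* No section says this. It would be a forecast of later wording.
- *The paediatric sample is too small to reveal a problem.* That depends on the rate. At an assumed 10%, 25 children have a 1 − 0.072 = 93% chance of showing at least one event. At 5% the figure is 1 − 0.277 = 72%. No rate is given as the one that matters.
- *FEV1 falls should be a safety proportion too.* Under Protocol 8.3, spirometry during the challenge is done only after asthma symptoms or a PEF fall of more than 20%, so FEV1 falls are not ascertained in everyone.

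**Conclusion.** The point holds as a gap in how a co-primary outcome is reported. The plan poses a safety question in groups of 10 and 25 and attaches no uncertainty to the answer, while using a suitable exact method for the other primary outcome. For infrequent events, none observed would leave true rates of up to 30.8% in adults and 13.7% in children compatible with the data.

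Those limits assume one yes/no outcome per participant, independence between participants, and the planned numbers being reached; fewer participants would widen them. The no-event probabilities rest on assumed rates of 5% to 20%. Since no acceptable rate is pre-specified, an interval turns the result into an honest estimate. It does not supply a pass or fail criterion, and the report should not suggest that it does. The change is a cheap improvement to reporting; it affects no procedure, sample size or stopping rule.

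**What to change.** In Protocol 13.4.2 and SAP 8.2, add exact two-sided 95% Clopper-Pearson intervals for the proportion of participants with:
1. at least one related AE;
2. at least one SAE;
3. a PEF fall of more than 20% from baseline, which SAP 8.2 already names and which Protocol 8.3 measures after every dose.

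For item 3, say whether falls with an FEV1 of at least 85% of baseline are counted, since Protocol 12.3.1 does not treat those as AEs.

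Give the intervals separately for Phase 1a, Phase 1b and Phase 2, following SAP 8.1. Note beside the Phase 1b figures that they come from a re-challenge of adults selected for tolerating Phase 1a (Protocol 4.2 and 4.3), so they are not a second independent sample. Use the number re-challenged as the Phase 1b denominator; it may be below 10.

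Report the safety result as an estimate with its upper limit, and state that zero events excludes only rates above that limit. Bring the label for safety in Protocol 13.1 into line with the other sections.

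The cost is a few more table entries, with item 3 needing its own row, and safety evidence that looks less favourable than a plain zero.

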13.4.3 Analyses of Secondary and Other Outcomes

The secondary statistical analyses will include summary statistics for the secondary endpoints and correlation analyses. Changes from baseline levels of TNSS, PNIF, and PEF will be estimated in absolute and relative terms.

To assess reproducibility of the adult nasal challenge, the first dose at which a positive response occurs for an individual will be compared between study visits. A weighted Kappa statistic and associated 95% confidence interval will be estimated for each dose category to quantify agreement between study visits.

13.5 Interim Analyses

Not Applicable.

13.6 Sample Size Considerations

This pilot study is powered based on the first primary outcome, the prevalence of positive response to NAC at each dose, defined as a sneezing score of 3 or TNSS ≥ 8 out of 12 in Phase 1 or TNSS ≥ 6 out of 12 in Phase 2. Because no preliminary data exists for this pilot study, the first primary objective of the analysis will be to estimate the probability of response at each of the 9 doses in the 10 subjects in Phase 1.

The table below summarizes the probabilities of observing a given number of responses for a given dose, along with exact 95% confidence intervals.

Number of observed responses at given dose (out of 10 subjects)	Probability of Response (95% CI)
0	0 (0.00, 0.31)
1	0.1 (0.003, 0.45)
2	0.2 (0.03, 0.56)
3	0.3 (0.07, 0.65)
4	0.4 (0.12, 0.74)
5	0.5 (0.19, 0.81)
6	0.6 (0.26, 0.88)
7	0.7 (0.35, 0.93)
8	0.8 (0.44, 0.97)
9	0.9 (0.55, 1.00)
10	1 (0.69, 1.00)

The proposed sample size for phase 2 of this protocol is 25 cockroach-sensitive children. Each participant will receive the optimal range of doses found in phase 1. The sample size of 25 children was chosen to provide further information about appropriate dosing levels.

14. Identification and Access to Source Data

14.1. Source Data

Source documents and source data are considered to be the original documentation where subject information, visits consultations, examinations and other information are recorded. Documentation of source data is necessary for the reconstruction, evaluation and validation of clinical findings, observations and other activities during a clinical trial.

14.2. Access to Source Data

The site investigators and site staff will make all source data available to the IND sponsor (DAIT/NIAID), as well as to relevant health authorities. Authorized representatives as noted above are bound to maintain the strict confidentiality of medical and research information that may be linked to identified individuals.

15. Protocol Deviations

15.1. Protocol Deviation Definitions

Protocol Deviation – The investigators and site staff will conduct the study in accordance to the protocol; no deviations from the protocol are permitted. Any change, divergence, or departure from the study design or procedures constitutes a protocol deviation. As a result of any deviation, corrective actions will be developed by the site and implemented promptly.

Major Protocol Deviation (Protocol Violation) - A Protocol Violation is a deviation from the IRB approved protocol that may affect the subject's rights, safety, or well-being and/or the completeness, accuracy and reliability of the study data. In addition, protocol violations include willful or knowing breaches of human subject protection regulations, or policies, any action that is inconsistent with the NIH Human Research Protection Program's research, medical, and ethical principles, and a serious or continuing noncompliance with federal, state, local or institutional human subject protection regulations, policies, or procedures.

Non-Major Protocol Deviation - A non-major protocol deviation is any change, divergence, or departure from the study design or procedures of a research protocol that does not have a major impact on the subject's rights, safety or well-being, or the completeness, accuracy and reliability of the study data.

15.2. Reporting and Managing Protocol Deviations

The study site principal investigator has the responsibility to identify, document and report protocol deviations. However, protocol deviations may also be identified during site monitoring visits or during other forms of study conduct review.

Upon determination that a protocol deviation (major or minor) has occurred, the study staff will a) notify the PI, b) notify the NIAID Medical Monitor and Project Manager, c) notify the SACC, and d) complete the Protocol Deviation form. The Protocol Deviation (PD) form will document at a minimum the date PD occurred, the date PD identified, a description of event, whether the deviation resulted in SAE/AE, the signature of PI, and documentation of a corrective action plan. The SACC and the IND sponsor (DAIT/NIAID) may request discussion with the PI to determine the effect of the protocol deviation on the study participant and his/her further study participation, the effect of the protocol deviation on the overall study, and corrective actions. The PI will complete and sign the Protocol Deviation form and submit it to the appropriate review bodies (SACC, DAIT/NIAID, and the central IRB, per IRB regulations). Protocol deviations will be reported to the DSMB and the central IRB.

16. Ethical Considerations and Compliance with Good Clinical Practice

16.1. Quality Control and Quality Assurance

The investigator is required to keep accurate records to ensure that the conduct of the study is fully documented. The investigator is required to ensure that all CRFs are completed for every participant entered in the trial.

The sponsor is responsible for regular inspection of the conduct of the trial, for verifying adherence to the protocol, and for confirming the completeness, consistency, and accuracy of all documented data.

The CRFs will be completed online via a web-based electronic data capture (EDC) system that has been validated and is compliant with Part 11 Title 21 of the Code of Federal Regulations. Study staff at the site will enter information into the electronic CRFs, and the data will be stored remotely at a central database. Data quality will be ensured through the EDC system's continuous monitoring of data and real-time detection and correction of errors. All elements of data entry (i.e., time, date, verbatim text, and the name of the person performing the data entry) will be recorded in an electronic audit trail to allow all changes in the database to be monitored and maintained in accordance with federal regulations.

